### 3.9 Statistical Analysis

Where not specified, we will use an Intention-to-treat (ITT) analysis approach, meaning all participants will be included in the analyses according to their randomised allocation.

#### Primary analyses:

- Repeated measures analyses (using a mixed effects linear regression model with a random effect on participant) will be used to compare primary outcomes across follow-up points. Baseline SDQ scores will be included as covariates. The primary endpoint is the intervention difference at 1 month. As multiple analyses are performed to compare both the experimental interventions and the active control with the control, and to compare the experimental intervention with the active control, a multiplicity adjustment will be made with a Bonferroni correction. We will also carry out sub-analyses of primary outcomes based on participants' demographic characteristics/adding them as covariates in the MLM.

Secondary analyses:

- The same modelling approach as primary analyses will be used for secondary outcomes where possible.
- A Complier Average Causal Effect (CACE) analysis will be used to provide an estimate of intervention effect, accounting for pre-specified per-protocol adherence and compliance with the intervention while retaining the benefits of randomisation. Such models will be performed for the primary and secondary outcomes at 1-month follow-up using observed data only and will include the covariates adjusted for in the regression models.
- The pattern of missing outcomes will be examined, and multiple imputations will be used to impute primary and secondary continuous outcomes. Imputation models will be informed by treatment arm, baseline scores, other covariates to be included in the model, and other baseline characteristics found to predict outcome or propensity for missingness (logistic regression models will be used to investigate the associations between baseline characteristics and missingness). Results of imputed models will be compared to the primary analysis complete case ITT models. We will carry out sensitivity analyses to estimate the intervention effect, including all missing data.
- We will estimate the causal effect of the intervention using two-stage least squares (2SLS) regression to account for potential endogeneity in nudge exposure. Random assignment to treatment group (T1 or C2 vs. control) will be used as an instrument for actual exposure. The first stage will model nudge exposure as a function of assignment; the second stage will regress the outcome on predicted exposure. This approach will yield a local average treatment effect (LATE) among compliers. Robust standard errors will be used throughout.
- Mediation analyses using structural equation modelling or parametric regression models will be carried out to gain insight into the mechanisms that could explain the potential effect of the interventions on primary outcomes.

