#### 2. STUDY OBJECTIVES

#### Primary objective:

 To examine the effectiveness of personalised AI nudges (experimental intervention) vs non-personalised digital self-help using generic CBT principles (active control) vs self-monitoring control on reducing CYP Strengths and Difficulty Questionnaire (SDQ) scores (primary outcome) at 1-month follow-up

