#### Secondary objectives:

- To examine the effectiveness of personalised AI nudges vs non-personalised digital self-help using generic CBT principles vs self-monitoring control on secondary outcomes [Eating Disorder Diagnostic Scale (EDDS); Sleep Condition Indicator Questionnaire (SCI); Self-Injurious Thoughts and Behaviours Interview (SITBI); Self-Efficacy Questionnaire for Children (SEQ-C); World Health Organisation-Five Well-Being Index (WHO-5)] at 1-month follow-up
- To examine the efficacy of personalised AI nudges on improving mental health in CYP in a low-risk group (primary prevention) and reduce poor mental health in a high-risk group (secondary prevention) at 1-month follow-up
- To explore potential mediators and moderators of beneficial effects of Al nudges

**Hypothesis**: Al nudges will be more effective than non-personalised digital self-help using generic CBT principles (active control group) and self-monitoring control at reducing CYP SDQ scores at 1-month follow-up

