### 3.8 Sample Size

The sample size for the internal pilot was 50 participants per group, defined a priori. A power analysis using the observed effect size from our internal pilot interim analyses (average Cohen's d = 0.137; f = 0.139) suggested that a total of 505 participants (168 per group) would be needed to detect between-group differences with 80% power at  $\alpha$  = .05. After adjusting for an anticipated 40% attrition rate, this increases to 842 participants (281 per group). However, our sub-analysis of high-risk participants showed a substantially larger effect size (average Cohen's d = -0.419; f = 0.462), suggesting that a smaller sample may be sufficient to detect meaningful intervention effects in this group. The sample size is an estimate and may differ from the actual sample size.

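### Plain Bonferroni over three pairwise contrasts is valid but needlessly strict for a hypothesis that AI nudges beat both comparators, and the primary result is not tied to that hypothesis

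*Protocol*

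**What the plan says.** Section 2 gives the primary objective as a three-way comparison, AI nudges "vs non-personalised digital self-help using generic CBT principles (active control) vs self-monitoring control on reducing CYP Strengths and Difficulty Questionnaire (SDQ) scores", without ranking the pairs. The hypothesis at the end of section 2 is more specific: AI nudges "will be more effective than non-personalised digital self-help using generic CBT principles (active control group) and self-monitoring control".

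Section 3.9 defines the primary analyses as those that "compare both the experimental interventions and the active control with the control, and to compare the experimental intervention with the active control". These are three contrasts: AI vs self-monitoring, generic vs self-monitoring, and AI vs generic. For these, "a multiplicity adjustment will be made with a Bonferroni correction". The split is not spelled out, but plain Bonferroni with no ranking means .05/3 = .0167 each. On the endpoint it says: "The primary endpoint is the intervention difference at 1 month", naming neither the intervention nor the comparator.

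Section 3.8 sizes the trial "to detect between-group differences with 80% power at" an unadjusted .05. It reports an "average Cohen's d = 0.137; f = 0.139) suggested that a total of 505 participants (168 per group) would be needed". That calculation names no pairwise contrast either.

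**The concern.** The hypothesis is about two contrasts, both containing the AI arm. The correction is spread over three, one of which (generic vs self-monitoring) does not contain it. Bonferroni protects a claim of the form *at least one of three*. The hypothesis, read naturally, is *both of two*, and a both-must-win claim needs no split of alpha between its parts. Each AI contrast is therefore held to .0167 when a less strict rule would protect equally well against error.

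Two things are at stake. The first is power for the trial's own hypothesis, lost without any gain in validity. The second is interpretation: nothing in section 3.9 connects the primary result back to the two-part hypothesis. The active control uses the same format as the AI nudges (section 3.3), so AI vs generic is the contrast that isolates personalisation. AI vs self-monitoring does not.

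**Working it through.** **Inputs.** Three arms, 1:1:1 (section 3.2). 505 evaluable participants, 168 per group, f = 0.139, d = 0.137, 80% power, alpha .05, 40% attrition (section 3.8). Three contrasts under Bonferroni (section 3.9). Assumed because not stated: SD 1, normal theory, no gain from baseline SDQ adjustment, two-sided tests with wins counted in the direction of benefit.

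**Step 1: reproduce the plan's sample size.** Take an omnibus one-way F test with three groups and noncentrality N × f². With f = 0.139, alpha .05 and power .80, N = 501.7, so 502. Power at 505 is 80.3%. For attrition, 505 / 0.60 = 841.7, so 842. The stated figures reproduce as an omnibus test.

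**Step 2: effect sizes.** The pattern of arm means is not given, so a range is used. If one arm differs from the other two by δ, the variance of the three means is 2δ²/9. Then f = δ√2/3 and δ = 0.139 × 3/√2 = 0.295. The stated d = 0.137 is taken as the lower value.

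**Step 3: a single contrast.** The standard error is √(2/168) = 0.1091. Critical values are 2.394 (.0167) and 1.960 (.05).
- δ = 0.295: expected z = 0.295/0.1091 = 2.704. Power is Φ(2.704 − 2.394) = 62% at .0167 and Φ(2.704 − 1.960) = 77% at .05.
- δ = 0.137: expected z = 1.256. Power is Φ(1.256 − 2.394) = 13% at .0167 and Φ(1.256 − 1.960) = 24% at .05.

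**Step 4: winning both AI contrasts when only AI works.** The two contrasts share the AI arm, so their correlation is 0.5. The joint probabilities were simulated.

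| Rule | δ = 0.295 | δ = 0.137 |
|---|---|---|
| Bonferroni, .0167 each | 46% | 5% |
| Step-down: largest contrast at .0167, then the other two at .05 | 62% | 9% |
| Both AI contrasts at .05, joint claim only | 65% | 11% |

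**Step 5: error control of the alternatives.** With three arms, if one pair truly differs, at most one of the other two pairs can be equal. After a correct first rejection only one true null can remain, and testing it at .05 is safe. The simulated family-wise rate of the step-down is 4.4% when all arms are equal, and 5.0% when two arms are equal and the third is far away. Anything Bonferroni rejects, the step-down also rejects. For the joint claim at .05 each, the worst case is AI equal to generic with both far above self-monitoring. The false joint claim rate there is 2.5%.

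**The case against.** **Bonferroni is valid and fits the objective.** This stands. The primary objective compares all three arms, so the three contrasts match it, and generic vs self-monitoring is not a stray test. The family-wise rate is protected. The point is about efficiency and fit to the hypothesis, not about inflated error.

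**A reader might infer something stronger:** that the plan lets a trial in which personalisation adds nothing be declared positive. With both nudge arms 0.295 SD better than self-monitoring and equal to each other, at least one primary contrast is significant in 78% of simulated trials (21% at 0.137). The documents do not support that reading. The 78% is almost entirely power to detect real differences from self-monitoring. AI vs generic itself comes out falsely in favour of AI in only 0.8%. Section 1.2 states the aim as the effectiveness of AI nudges, not the increment from personalisation, so AI vs self-monitoring bears directly on it. The protocol nowhere says that any one significant contrast makes the trial positive. If the hypothesis is a conjunction, it already implies that one win does not confirm it.

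**The success rule can sit in the SAP.** Partly right: its absence alone would be no finding. But the protocol itself fixes the contrasts and the correction, and a SAP that followed them would carry the loss of power over.

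**The alternatives do not rescue power.** Also right. Even at 0.295 SD the joint rule has 65%, short of 80%. Reaching 80% would take about 225 completers per arm at 0.295, or about 1,043 at 0.137.

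**Conclusion.** The concern holds as a matter of efficiency and clarity. The stated correction is valid but stricter than the hypothesis requires, and the endpoint wording leaves the primary result unconnected to it. Moving to the step-down raises the chance of winning both AI contrasts from 46% to 62% at 0.295 SD, and from 5% to 9% at 0.137, with the same family-wise protection. Testing only the joint claim gives 65% and 11%.

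These figures rest on 168 completers per arm, an effect in the AI arm alone and no covariate gain. Adjustment for baseline SDQ would raise all of them by an amount the protocol does not allow one to compute. The 0.295 depends on an assumed pattern of means.

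A further inference to avoid is that a win over self-monitoring without a win over generic nudges shows that personalisation adds nothing. A non-significant contrast does not show that. If AI truly beats both by 0.295 SD and each is tested at .05, AI beats self-monitoring but not generic in 77.1% − 64.9%, about 12%, of trials. Calling those trials evidence of no personalisation effect would be wrong.

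**What to change.** In section 3.9:

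1. Replace plain Bonferroni with the step-down procedure for three pairwise comparisons: test the contrast with the smallest p-value at .0167 and, if it is rejected, the other two at .05 each.
2. State that the section 2 hypothesis is confirmed only if AI nudges are superior to both the active control and self-monitoring at 1 month. If only this joint claim is wanted, each of the two contrasts can be tested two-sided at .05 with no split, and generic vs self-monitoring becomes secondary.
3. State that a win over self-monitoring alone will be reported as not establishing a benefit of personalisation, together with the AI vs active control estimate and its confidence interval, and not as evidence that personalisation adds nothing.

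The cost is a few sentences, best settled before any unblinded main-trial results exist. The change itself needs no further data or participants, though it does not bring the both-win power to 80%. Simultaneous confidence intervals that match step-down tests are less simple than Bonferroni intervals, and a single win can no longer be presented as confirming the hypothesis.

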### 3.6 Baseline and Follow-Up Assessments

The baseline assessment consists of web-based self-reported validated mental health measures and demographic information (see Outcomes):

- Screening Measures: Mood Disorder Questionnaire (MDQ); Screening to Brief Intervention (S2BI). MDQ and S2BI questionnaires will be used to characterise the sample.
- Primary Outcomes: Strengths and Difficulties Questionnaire (SDQ)

- Secondary Outcomes: Eating Disorders Diagnostic Scale (EDDS); Sleep Condition Indicator Questionnaire (SCI); Self-Injurious Thoughts and Behaviours Interview (SITBI); Self-Efficacy Questionnaire for Children (SEQ-C); World Health Organisation- Five Well-Being Index (WHO-5)
- Demographics: age, gender, sexual orientation, ethnicity, education level, socioeconomic status, location (school)
- Presence of learning difficulties, organic brain disease, or severe neurological impairment that prevents independent use of smartphone app (yes/no)

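### The moderator objective has no analysis that tests whether the arm effect differs between groups: section 3.9 offers only demographic sub-analyses or demographic covariates

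*Protocol*

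**What the plan says.** Section 2 (Secondary objectives) includes an aim to "explore potential mediators and moderators of beneficial effects" of the AI nudges. A separate secondary objective concerns the effect "in a low-risk group (primary prevention) and reduce poor mental health in a high-risk group (secondary prevention) at 1-month follow-up".

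Section 3.9 gives the mediator half its own method: "Mediation analyses using structural equation modelling or parametric regression models will be carried out". For moderators it names none. The one sentence that could serve is in the primary-analysis paragraph and promises "sub-analyses of primary outcomes based on participants' demographic characteristics/adding them as covariates in the MLM".

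The primary model in that paragraph is a mixed linear regression with baseline SDQ as a covariate, and a Bonferroni correction covers the three pairwise arm comparisons. No arm-by-characteristic term appears anywhere in the protocol. Section 3.6 lists seven demographic characteristics, including school. Baseline SDQ risk is not among them, so the demographic sentence does not cover it.

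**The concern.** A moderator question has a specific null hypothesis: the arm difference in SDQ is the same at every level of the characteristic. Neither named route has that null.

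- **Covariate route.** A demographic entered as a main effect is tested for association with 1-month SDQ after adjustment for baseline SDQ. The model assumes one common arm effect, so a real moderator has no parameter in which to appear.
- **Subgroup route.** A model fitted within a group tests for no arm effect in that group. Two such results, one significant and one not, do not compare the two effects. A shared effect with halved samples produces that pattern readily.

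At stake is the claim about who benefits. Section 3.8 already leans on this kind of comparison. It sets a larger effect size in high-risk pilot participants (d = -0.419) beside the overall figure (d = 0.137) and reports no test of the difference. The primary endpoint is not affected.

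**Working it through.** **Inputs from the protocol.** Section 3.8: "a total of 505 participants (168 per group) would be needed to detect between-group differences", based on "average Cohen's d = 0.137; f = 0.139", with 80% power, alpha .05 and 40% attrition. Section 3.9: Bonferroni over three comparisons, .05/3 = .0167.

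**Assumptions of this check.** One two-arm contrast, two-sided tests, outcome SD of 1, a binary characteristic, and an identical true effect in both groups. Residual SD is either 1 (no baseline adjustment) or sqrt(1 - 0.6²) = 0.8 (baseline correlation 0.6, assumed; the protocol gives none).

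**1. The plan's own figure.** One-way F test, three groups, noncentrality N·f², f = 0.139, alpha .05: 80% power needs N = 502, and N = 505 gives 80.3%. Attrition: 505/(1 - 0.4) = 842. The stated sizes reproduce, so 168 analysed per arm is used below.

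**2. Chance that exactly one of two equal halves is significant at .0167.** Each half has 84 per arm.
- λ = d·sqrt(84/2)/SD = 6.481·d/SD
- p = Φ(λ - 2.394) + Φ(-λ - 2.394)
- P(exactly one) = 2p(1 - p)

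| d | Residual SD | λ | p per half | Exactly one |
|---|---|---|---|---|
| 0.137 | 1 | 0.888 | 0.067 | 12% |
| 0.137 | 0.8 | 1.110 | 0.100 | 18% |
| 0.278 | 1 | 1.802 | 0.277 | 40% |
| 0.278 | 0.8 | 2.252 | 0.444 | 49% |
| 0.3 | 1 | 1.944 | 0.326 | 44% |
| 0.3 | 0.8 | 2.430 | 0.514 | 50% |
| 0.4 | 1 | 2.592 | 0.579 | 49% |
| 0.4 | 0.8 | 3.240 | 0.801 | 32% |

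Of these effects, only 0.137 is the protocol's stated whole-sample d. The value 0.278 is 2f, a conversion assumed here that does not agree with the stated d. The values 0.3 and 0.4 are benchmarks.

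**3. Uneven groups.** With a 20:80 split, P(exactly one) = p(1 - q) + q(1 - p). At .0167 this gives 13% (SD 1) to 19% (SD 0.8) at d = 0.137, and 52% to 65% at d = 0.3.

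**4. Interaction test.** With no true moderation it rejects at its nominal 5%. In 20,000 simulated trials (d = 0.278, equal halves, no baseline adjustment) it rejected in 4.9%. In the same trials exactly one half was significant at .05 in 49%.

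**5. Several characteristics.** Seven independent interaction tests at .05 give 1 - 0.95⁷ = 30% for at least one false positive, so an interaction term alone does not settle multiplicity.

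**6. Power of the interaction test.** For a difference in effect of 0.278 between equal halves, without baseline adjustment, SE = 2·sqrt(2/168) = 0.218. Power is Φ(0.278/0.218 - 1.96) = about 25%. For 80% power, n per arm = 8·(1.960 + 0.842)²/0.278² = about 813 analysed.

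**The case against.** **The link is inferred.** The demographic sentence sits under the primary analyses and does not mention moderators. If the two are unconnected, the protocol merely names no method for an exploratory objective, which could be left to a statistical analysis plan not seen here. This stands as a limit. It does not remove the point, because the protocol states a demographic analysis, that analysis is the only candidate, and a later plan that followed it would inherit the mismatch.

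**The sentence does not prescribe a bad decision rule.** It does not require separate models, significance tests per group, or a verdict of moderation when only one group is significant, and it does not exclude interactions. That is correct. The percentages above apply only if someone reads a split result as moderation.

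**A reader might infer that the covariate route also produces false moderators.** The documents do not support that. A significant demographic main effect, if a real group difference remains after baseline adjustment, is a correct finding about the outcome level. How often it is significant is power for that difference, not a false-moderation rate. Because baseline SDQ is in the model, a follow-up gap fully explained by baseline would be flagged at only about 5%. The fault of this route is that it gives no answer on moderation.

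**At the stated d the problem is smaller.** This stands: 12-18% at d = 0.137 with equal halves.

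**Conclusion.** The point holds as a mismatch between objective and method. Section 2 asks about moderators, and neither analysis named in section 3.9 estimates or tests a difference in arm effect. If discordant subgroup significance is read as moderation, an effect shared by everyone would appear moderated in about 12-18% of trials at d = 0.137 and 44-50% at d = 0.3. Those figures are per binary characteristic, at .0167, with equal halves and 168 analysed per arm. An interaction test at .05 gives 5%. The ranges rest on the assumed baseline correlation (0 to 0.6), and uneven groups raise them.

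It would go too far to say that the protocol commits the trial to false moderator claims, or that its covariate models inflate error. The objective is exploratory and the primary comparison is untouched. The change is worth making because the named method cannot answer the question and the replacement is standard.

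**What to change.** Replace the demographic sentence in section 3.9 with text along these lines:

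*Moderation will be examined in all participants by adding the characteristic and its interaction with arm to the primary model, for baseline SDQ risk and for a short list of demographics named before analysis. Interaction estimates will be reported with 95% confidence intervals. Subgroup effects will be derived from this model and are descriptive. No moderator claim will rest on a covariate main effect or on significance in one subgroup only. These analyses are exploratory and not controlled for multiplicity.*

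Baseline risk belongs in the list because section 2 names those groups itself. Keep the model with demographics as main effects only, described as a covariate-adjusted sensitivity analysis of the primary contrast.

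**Cost.** No new data are needed, since the characteristics are collected at baseline. The list should be short: with three arms, a binary characteristic adds two interaction terms, whereas school, at the 5-10 schools planned in section 3.4, adds 2 × 4 = 8 to 2 × 9 = 18. The main downside is power, about 25% for an interaction of 0.278 SD without baseline adjustment, so fewer results will look positive and a null interaction will not show that effects are equal.

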During this time, the Principal Investigator will be custodian for the data archived following the Imperial College London archiving procedures. The Principal Investigator will preserve the confidentiality of participants taking part in the study and fulfil transparency requirements under the General Data Protection Regulation for health and care research.

Participants will be able to withdraw from the study at any point up until data analysis has commenced by contacting the research team at [contact]. All data will be deleted from Imperial College London network drives. If the participant grants consent, any anonymised data collected up to the point of withdrawal will be used. Participants will not be able to withdraw their data after the results have been published, as data will be anonymous and will not be linked to the participant.

Anonymised data may be made available to other researchers after the end of the study via data repositories such as Open Science Framework and disseminated through peer-reviewed journals and conference presentations. This will be explained to participants in the Participant Information Sheet and Informed Consent form.

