#### 4.4. WITHDRAWAL CRITERIA

Participants will be able to withdraw from the study at any point up until data analysis has commenced by contacting a member of the research team via email at [contact]. Any anonymised data collected up to the point of withdrawal will be used.

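### The primary analysis is labelled intention-to-treat but is complete case at 40% expected attrition, and imputation from arm and baseline variables alone is a weak check on it

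*Protocol*

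**What the plan says.** Section 3.9 of the protocol makes intention-to-treat the default where nothing else is specified, and explains that "all participants will be included in the analyses according to their randomised allocation". The primary model is a mixed-effects linear regression with a random participant effect and baseline SDQ as a covariate; the endpoint is the difference at 1 month.

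Multiple imputation stands among the secondary analyses, as a comparator: "Results of imputed models will be compared to the primary analysis complete case ITT models". Its predictors are listed: "Imputation models will be informed by treatment arm, baseline scores, other covariates to be included in the model, and other baseline characteristics", the last of these being ones found to predict outcome or missingness. Missingness itself is to be modelled on baseline characteristics. A further sensitivity analysis is to take in all missing data, but no method is named.

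Section 3.8 expects heavy loss: "After adjusting for an anticipated 40% attrition rate, this increases to 842 participants". Section 3.5 gives one follow-up, at 1 month. Sections 3.2 and 3.7 show that all arms are asked to enter data daily for four weeks, with eight required trackers, and that days of app access are recorded.

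On withdrawal, Section 3.10 says "All data will be deleted from Imperial College London network drives" and allows anonymised data to be used if the participant consents. Section 4.4 says "Any anonymised data collected up to the point of withdrawal will be used", with no condition.

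**The concern.** One analysis carries two labels that cannot both apply when outcomes are missing. Either all randomised participants enter the primary estimate or only those with a 1-month SDQ do.

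The choice matters because the expected loss is large and could plausibly depend on arm and on post-baseline state. Section 3.2 lists participants in the intervention and active control groups as blind, but not those in the self-monitoring arm. Section 3.12 provides for nudges to be disabled when a participant worsens, which alters the app only in arms that receive nudges. A baseline covariate captures neither. If such mechanisms act, the complete-case difference is biased. Imputation from baseline variables would tend to agree with it, and that agreement would be read as reassurance.

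**Working it through.** **1. The plan's own figures.** Inputs from Section 3.8: f = 0.139, alpha 0.05, power 80%, 505 evaluable, 40% attrition, 842 randomised. A one-way F test with three equal groups (noncentral F) needs N = 502 at f = 0.139 and 506 at f = 0.1385; power at 505 is 80.3%. Then 505 / (1 − 0.40) = 841.7, or 842. The figures reproduce, and the trial is sized in completers.

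**2. Who drops out of the primary estimate.** 842 × 0.60 = 505 remain and 842 × 0.40 = 337 leave. The mixed model does not recover them: with one follow-up and baseline SDQ used as a covariate, each participant has at most one outcome row, and a participant without a 1-month SDQ has none.

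**3. The benchmark for bias.** With three equal groups, f = 0.139 fixes the largest pairwise difference within a range:
- middle arm halfway between the others: 0.139 × √6 = 0.340 SD
- two arms equal and one apart: 0.139 × 6/√8 = 0.295 SD

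**4. Size of the bias.** Within an arm, the completer mean minus the full mean equals (share missing) × (completer mean − non-completer mean, given baseline). Assuming 40% missing in every arm, the bias in a between-arm difference is 0.40 × Δ, where Δ is the between-arm difference in that gap.

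| Δ (assumed, SD) | Bias (SD) |
|---|---|
| 0.1 | 0.04 |
| 0.2 | 0.08 |
| 0.3 | 0.12 |

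This runs from 0.04/0.340 = 12% to 0.12/0.295 = 41% of the largest pairwise difference. If Δ = 0, so that the gap is the same in every arm, the bias is nil.

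**5. Whether the planned imputation would reveal it.** Imputing from arm and the covariates already in the model gives the complete-case estimate in expectation. Extra baseline predictors help only with missingness that baseline explains. An illustrative simulation used two arms of 281 with about 40% missing, and missingness in the experimental arm depended on an in-trial app-reported state known for everyone:

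| Analysis | Mean estimate (SD) |
|---|---|
| True effect | −0.137 |
| Complete case | −0.225 |
| Imputation, arm and baseline | −0.225 |
| Imputation, app state added | −0.137 |

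The scenario was built to show the mechanism and favours the app variable. It does not predict this trial's bias.

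**6. Precision.** If auxiliaries explain a share R² of the residual SDQ variance and are available for every non-completer, effective n = 842 / (R² + (1 − R²)/0.60). That is 505 at R² = 0, 561 at R² = 0.25 and 601 at R² = 0.40. The R² values are assumed, and incomplete tracker data lower the result.

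**7. Withdrawal, side by side.** Section 3.10 makes use of data collected before withdrawal depend on consent; Section 4.4 does not. Section 3.3 also lets users withdraw inside the app, whereas 3.10 and 4.4 describe contacting the research team. The rule decides which data exist for any all-randomised analysis.

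**The case against.** The strongest reply is that the intention-to-treat sentence is only a default, so a complete-case primary analysis may be a permitted exception. That softens the conflict. It does not remove it, because the exception is itself still called intention-to-treat.

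Imputation predictors are also often settled in a statistical analysis plan, which is not shown. That is fair, and leaving out tracker data is not an error. But the protocol gives its own list, which names no in-trial variable, so adding them is a worthwhile improvement. School is already a baseline variable (Section 3.6) and needs no new rule. The further sensitivity analysis means imputation is not the only safeguard, but without a method it cannot be relied on. Running the complier analysis on observed data is an openly stated secondary choice and contradicts nothing.

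A reader might infer that the bias could equal the effect the trial was sized on, since Section 3.8 also quotes d = 0.137 and 0.40 × 0.3425 = 0.137. The protocol does not support that. The 505 follows from f = 0.139; a pairwise d of 0.137 would need about 837 per group at alpha 0.05. A bias of 0.137 SD is about 40% to 46% of the implied largest difference. Matching that difference would take Δ of 0.295/0.40 = 0.74 to 0.340/0.40 = 0.85 SD, and no figure for Δ is given.

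A reader might also infer that app data are the best description of those who drop out. The SDQ comes from a separate online questionnaire (Section 3.5), so stopping the app and missing the outcome are different events. Section 3.8 does not define its 40%, and non-completers may have few entries.

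**Conclusion.** The point holds as a labelling conflict within Section 3.9 and a weak missing-data plan for the attrition expected. About 337 of 842 randomised participants would leave the primary estimate. That figure rests only on the protocol's own numbers and a single outcome row per participant. The planned comparison would largely repeat the complete-case answer if missingness depends on post-baseline state.

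The bias range of 0.04 to 0.12 SD rests on assumed gap differences of 0.1 to 0.3 SD and equal 40% attrition by arm. Its actual size and direction cannot be derived from the protocol. Confidence is high for the textual conflict and low for the amount of bias.

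The withdrawal conflict is separate. A reader might conclude that data should be kept by default after withdrawal, but that is a consent and data-protection question in a sample that includes under-16s, and nothing here settles it. Nor does the protocol show that formal withdrawal, as opposed to non-response, drives the 40%.

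**What to change.** - Define the primary intention-to-treat estimate as covering all randomised participants through multiple imputation carried out by arm. Report complete case as a sensitivity analysis.
- Keep the baseline predictors and add, as auxiliary variables, summaries of the eight required trackers (for example weekly means up to last use) and days of app use. Promoting imputation without in-trial variables would change little, as step 5 shows.
- Name the method of the sensitivity analysis for missing data, for example a delta adjustment.
- Reconcile Sections 3.10 and 4.4, together with the in-app route in Section 3.3, on the use of data after withdrawal. Which rule applies is for the sponsor and the ethics committee.

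The cost is extra analysis work and aligned wording, fixed before outcomes are seen; no new data are collected. The gain is limited for participants with few app entries, so an effective n of about 560 to 600 is an upper bound under the assumed R².
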